## **Stopping Rules**

We will perform semi-annual futility analyses using Bayesian predictive probability methods. These analyses would be timed to occur at the time of our annual DSMB review as well as mid-way in between the meetings. The more frequent interim futility analysis will allow us to determine in a more timely fashion when and if there is sufficient evidence that it is unlikely that we would conclude that one treatment was better than the other if we completed planned enrollment. Consideration should be given to stopping the trial early for futility if the predicted probability that a significant difference between glutamine and placebo would be observed in the trial if it were continued to completion is < 5%.

Separate analyses will be performed for the mTOR inhibitor patients and for the esophagus radiation patients.

The study statisticians will conduct the analyses and send the results to the DSMB for consideration. The PI will not be notified of the results of these analyses unless the DSMB determines to recommend that study enrollment be stopped.

### 12.5 Randomization and Blinding

Patients will be equally randomized between treatment arms using permuted blocks within strata separately for the two groups of patients. For patients who will receive mTOR inhibitor based therapy, randomization will be stratified by: prior mucositis (Y/N), and prior radiation therapy to the head and neck (Y/N). For patients who will

receive radiation to the esophagus, randomization will be stratified based on the volume of esophagus receiving 40 Gy: (1) 20-40%; (2) 41-60%; (3) 61-80%.

CORe will set up a Randomization website and the Investigational Pharmacy personnel will perform the randomization assignment.

Both patients and the research staff conducting the assessment will be blinded to the treatment assignment. Placebo powder identical to glutamine powder in appearance and taste will be compounded by Healios Nutrition Oncology, and both will be dispensed by Investigational Pharmacy at MD Anderson. At the end of the blinded phase, we will assess blinding by asking patients which study arm they believe they have been randomized to.

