# 2.1.2 Radiation and Esophagitis

More than 1.5 million new cases of cancer are expected to occur in the United States in 2010, including more than 200,000 new cases of lung cancer and 16,000 new cases of esophageal cancer. The primary aim of thoracic radiotherapy (TRT) in both NSCLC and esophageal cancer is to maximize the therapeutic ratio in order to deliver an effective dose to the tumor while maintaining an acceptable dose to the neighboring normal tissues. However, complications such as acute radiation-induced esophagitis (ARIE) may cause significant morbidity, unplanned treatment delays, and a decreased chance to escalate the dose to more effective levels. These issues may reduce tumor control and survival rates, as well as the patients' quality of life (QOL).

ARIE is often the dose-limiting complication that is reported in 5–100% of patients treated with TRT. Clinical and dosimetric factors that may be related to the incidence and severity of ARIE include: age, tumor and nodal stage, concurrent chemoirradiation, mean esophageal dose and maximal dose point, and esophageal volume receiving >35 Gray (Gy) (V35), V45, V50, V60, percent length of esophagus receiving >40 Gy, and >66 Gy full circumferences. Most of these factors are closely associated with the total radiation dose received by a certain volume of esophagus. Thus, to prevent ARIE, the dose to the esophagus must be kept under the organ tolerance level, which can possibly be achieved by complete exclusion of the esophagus from the RT field by using novel RT techniques, such as intensity modulated RT (IMRT). However, often this approach is not feasible due to the organ's central position in the mediastinum, and the proximity of involved lymph nodes relative to the esophagus. Therefore, the primary strategies in controlling ARIE currently revolve around identifying an effective radioprotective agent. Based on the significant prior data, review below (section 2.2 and 3.0) we believe that glutamine will prove to be a safe and effective radioprotector of the esophagus.

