# 4.0 Patient Eligibility

# 4.1 Inclusion Criteria

- Patients who will be initiating therapy with any investigator-initiated mTOR inhibitor based therapy in the Department of Investigational Cancer Therapeutics (Phase I Program) or initiating radiation therapy to the esophagus.
- For the esophagitis arm, any patient with thoracic malignancies, which will receive radiation alone or concurrent chemo/radiation. Radiation dose must be ≥ 45 Gy. For the esophagitis arm, induction chemotherapy is allowed.
- Ability to understand and the willingness to sign a written informed consent. A signed informed consent must be obtained prior to any study specific procedures.
- 4) Patients must be >/= 17 years of age.
- 5) Women of child-bearing potential MUST have a negative serum or urine pregnancy test unless prior hysterectomy or menopause (defined as 12 consecutive months without menstrual activity). Patients should not become pregnant or breastfeed while on this study. Sexually active patients must agree to use contraception prior to study entry, for the duration of study participation, and for 30 days after the last dose.

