# 4.2 Exclusion Criteria

1) Patients currently receiving therapy for mucositis.

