# 5.1.2 Radiation to the Esophagus

Radiation must be  $\geq$ 45 Gy delivered alone or with concurrent chemotherapy. The type of concurrent chemo will be determined by the treating physician. For the esophagitis arm, induction chemotherapy is allowed. XRT must be given using

conventional daily fraction dose from 180-240 cGy per day. Radiation technique may include: 3D conformal, IMRT, and or protons. Glutamine will start on the first day of radiation, or within 10 days of the start of radiation and will be continued for 4 weeks after the last day of radiation. Radiation will be given daily (Monday through Friday) for 5 days per week. The number of weeks of radiation therapy will be determined by the treating physician. The end of treatment week will vary based on the number of weeks of radiation that the patient receives.

[figure not shown]

Figure 3. Treatment Regimen (Schema)

For patients who will receive mTOR inhibitor based therapy: the patients will be randomized to receive either placebo or Glutamine beginning on Day 1 of an mTOR inhibitor based therapy.

**For patients who will receive radiation to the esophagus:** the patients will be randomized to receive either placebo or Glutamine beginning on Day 1 of radiation treatment, or within 10 days of the start of radiation.

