## 12.3 Sample Size

There will be a total of 180 patients in this study. The cohort of patients on mTORbased regimens will be 100, and the cohort of patients on radiation regimen will be 80.

For esophagus radiation, published data indicate that the distribution of patients by esophagitis grade is 0-1: 26%, 2: 37%, 3: 37% for patients not given glutamine. If we target a modest treatment effect (0-1: 50%, 2: 38%, 3: 12%) then 40 patients per treatment arm would give us 81% power (assuming a two-sided 5% alpha and use of the Wilcoxon rank sum test for analysis).

For mTOR inhibitor patients, we have unpublished data from 87 patients indicating that the distribution of patients by oral mucositis grade is 0-1: 69%, 2: 22%, 3: 9% for patients not given glutamine. If we target (0-1: 95%, 2: 5%, 3: 0%) as the results in the glutamine arm, then 50 patients per arm would give us 94% power (assuming a two-sided 5% alpha, and use of the Wilcoxon rank sum test for analysis).

These calculations were made using nQuery Advisor 7.0.

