### 12.4 Statistical Analysis Plan

Note: Analyses will be performed separately for patients treated with mTOR inhibitors and patients with esophagus radiation.

For the primary objective, we will use the Wilcoxon rank sum test to compare the ordered categories of mucositis/esophagitis severity between treatment arms. A patient must complete at least 60% of the planned doses of placebo or glutamine to be considered evaluable in the statistical analysis. As a sensitivity analysis for the appropriateness of 60% dosing cut-off, we will analyze the outcome according to the proportion of drug taken. The proportional of drug taken will be computed as the ratio of number of doses taken to the total number of doses prescribed. For the mTOR inhibitor group, the denominator will reflect the total time that each patient is on the study. For the esophagus radiation group, the denominator will reflect the total number of doses that are prescribed during the delivery of radiation.

For the secondary objectives/endpoints, we will compare between treatment arms (1) the trajectories of the mucositis/esophagitis scores over time using linear mixed effects; (2) the proportion of patients developing mucositis/esophagitis using a Pearson chi-squared test; (3) the proportion of patients developing grade 3 or higher mucositis/esophagitis using a Pearson chi-squared test; (4) the duration of mucositis/esophagitis using the Wilcoxon rank sum test; (5) the time to develop mucositis/esophagitis using Kaplan-Meier estimates and the log rank test (due to right censoring in patients not developing mucositis/esophagitis); (6) the proportion of patients having treatment interruptions using a Pearson chi-squared test; (7) the

weight change using the Wilcoxon rank sum test; and (8) the QOL survey scores using the Wilcoxon rank sum test.

For the secondary objective of describing the toxicity profile, descriptive statistics will be provided on the grade and type of toxicity by treatment arm.

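### The radiation cohort's esophageal V40 strata stop at 20% and 80% although eligibility sets no V40 limit, and the primary test does not use the strata

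*Combined protocol and SAP*

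**What the plan says.** Section 12.5 randomises 1:1 in permuted blocks within strata, separately for the two cohorts. For the radiation cohort there is one factor: "randomization will be stratified based on the volume of esophagus receiving 40 Gy: (1) 20-40%; (2) 41-60%; (3) 61-80" percent.

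Eligibility for that cohort is broad. Section 4.1 reads "For the esophagitis arm, any patient with thoracic malignancies, which will receive radiation alone or concurrent chemo/radiation" and adds a floor of 45 Gy on the radiation dose. The only entry in section 4.2 is "Patients currently receiving therapy for mucositis". Section 5.1.2 repeats the dose floor, sets the fraction size and states "Radiation technique may include: 3D conformal, IMRT, and or protons". None of these sections sets a lower or upper limit on the share of the esophagus receiving 40 Gy (V40).

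On the analysis, section 12.4 says "we will use the Wilcoxon rank sum test to compare the ordered categories of mucositis/esophagitis severity between treatment arms". It splits the analysis by cohort and mentions neither randomisation strata nor covariates. Section 12.3 sizes the radiation cohort at 40 per arm for 81% power with the same unstratified test at two-sided 5%.

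On prognosis, section 2.1.2 introduces its list with "Clinical and dosimetric factors that may be related to the incidence and severity of ARIE include". The list has several dose-volume and dose-length measures, and the section adds that most of them track the dose received by a given volume of esophagus. V40 by volume is not itself listed, and no effect size is given.

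**The concern.** There are two linked gaps.

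First, the three bands do not cover the eligible population. A patient below 20% or above 80% can be enrolled, but permuted blocks within strata need a stratum and none is defined. Someone would have to settle the matter case by case. Read literally, the whole-number limits also leave 40.5% or 60.5% unassigned unless V40 is rounded.

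Second, V40 is the only factor on which this cohort is balanced, and the primary test then ignores it. Stratified randomisation on a prognostic factor makes the arms more alike than simple randomisation would. A test that ignores the strata overstates the variance of the comparison, so its type I error falls below 5% and it gives up power. The validity of the trial is not at stake. What could be lost is efficiency in a cohort of 80 planned at 81% power, using information already collected.

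The gaps are linked because a stratified test, like the randomisation itself, needs every patient to have a stratum.

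**Working it through.** **1. The plan's own power figure.** Inputs from section 12.3: control grades 0-1/2/3 at 26/37/37%, glutamine 50/38/12%, n = 40 per arm, two-sided 5%.

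- Probability that a glutamine patient has the lower grade, plus half the ties: θ = 0.50 × (0.74 + 0.13) + 0.38 × (0.37 + 0.185) + 0.12 × 0.185 = 0.4350 + 0.2109 + 0.0222 = 0.6681.
- Tie-corrected null variance, with mean proportions 0.38, 0.375 and 0.245: v0 = (1 − Σm³)/12 × 2/n = (0.8777/12) × (2/40) = 0.003657, SE 0.0605.
- Variance under the alternative: v1 = (0.0532 + 0.0730)/40 = 0.003156, SE 0.0562.
- Power = Φ[(0.1681 − 1.96 × 0.0605)/0.0562] = Φ(0.88) = 81.1%.

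Simulation of the tie-corrected test also gives 81.1%. The stated 81% is sound.

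**2. Coverage of the bands.**

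| Source | Restriction on V40 |
|---|---|
| 4.1 Inclusion | none (dose floor of 45 Gy only) |
| 4.2 Exclusion | none |
| 5.1.2 Radiation | none (fraction size and technique only) |
| 12.5 Strata | defined from 20% to 80% only |

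The documents give no V40 distribution. For an assumed share outside 20-80%, the number without a stratum is 80 × 0.02 = 1.6, 80 × 0.05 = 4 or 80 × 0.10 = 8. If such patients were not randomised and not replaced, the formula in step 1 gives 79.0% power at 38 per arm (5% lost) and 76.7% at 36 per arm (10% lost).

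**3. Unstratified versus stratified test.** The van Elteren statistic sums (W − E)/(N + 1) over strata. W is the rank sum of one arm within the stratum, E its null expectation and N the stratum size. The sum is divided by the square root of the summed tie-corrected variances, each weighted by 1/(N + 1)².

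Simulation: N = 80, grade distributions fixed at the section 12.3 values, a proportional-odds shift between adjacent V40 bands, and 100,000 trials per setting. The odds ratio per band, the band shares and the block size of 4 are assumptions; none is in the documents. With equal bands:

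| OR per band | Unstratified power | van Elteren power | Difference (points) | Unstratified type I error |
|---|---|---|---|---|
| 1 | 81.2% | 80.9% | −0.3 | 5.0% |
| 1.5 | 81.5% | 82.2% | +0.7 | 4.7% |
| 2 | 81.9% | 84.4% | +2.5 | 4.1% |
| 3 | 83.4% | 89.0% | +5.6 | 3.0% |
| 4 | 84.3% | 91.9% | +7.6 | 2.2% |

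The type I error of van Elteren stays at 4.9-5.1%. With unequal bands the gain shrinks: with 50/30/20% shares the differences are −0.3, +0.6, +2.2, +5.1 and +7.2 points, and with 60/30/10% they are −0.3, +0.3, +1.5, +3.8 and +5.4.

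For the unstratified test to match van Elteren at N = 80 with equal bands takes about 2, 6, 13 and 19 more patients at OR 1.5, 2, 3 and 4.

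A second model, with a latent normal severity and a shift of 0, 0.5 or 1.0 SD per band, agrees in direction: 80.8% versus 80.5%, 82.6% versus 85.8%, and 85.5% versus 94.1%.

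**4. mTOR cohort.** The same comparison with N = 100, four strata and OR 1 to 2 gives differences of −0.2 to +0.8 points, which is not material.

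**The case against.** The strongest reply is that the choice of test is a preference. The Wilcoxon test is valid, errs on the conservative side and matches the sample size calculation. The gain depends wholly on an assumed V40 effect. At OR 1.5 per band or less it is under one point. Gains above five points with equal bands need about OR 3 per band, which is 3 × 3 = 9-fold between the lowest and highest bands, and with 60/30/10% bands OR 3 yields only 3.8 points. All of that stands. It makes this an efficiency improvement and not the correction of an error. It does not remove the imbalance between a cost of about 0.3 points and a possible gain of several.

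On the bands, section 2.1.2 mentions sparing the esophagus completely with IMRT, but it calls this often not feasible. A patient so treated is arguably not receiving radiation to the esophagus and so not in the cohort. That weakens this remark as evidence of how often V40 falls below 20%, and the documents offer nothing specific on values above 80%. Neither point closes the gap: partial sparing remains possible with the permitted techniques, and no eligibility rule refers to V40.

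Finally, the randomisation website may handle out-of-range values, but its specification is not in the documents. Placing a few patients in the nearest band before blinded allocation would affect balance slightly and would not bias the comparison. That is a fair limit on the consequence.

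**Conclusion.** Both parts hold on the text. Some eligible radiation patients have no stratum under section 12.5 as written; how many cannot be told from the documents. The primary test does not use the one factor on which the cohort is balanced. The planned 81% power is met and the false-positive rate is not inflated.

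The benefit of a stratified test is conditional: roughly 1.5 to 5.6 points of power if the odds ratio per band is 2 to 3 (60/30/10% to equal bands), and nothing, less about 0.3 points, if V40 is unrelated to grade. The plan's choice of V40 as the sole stratification factor makes some association plausible, but its size is an assumption. This is a change worth making because it is cheap; the trial does not fail without it.

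**What to change.** - **Section 12.5:** make the bands contiguous and exhaustive, for example 40% or less, over 40% to 60%, and over 60%. If V40 limits were intended, reconcile the eligibility criteria with the bands.
- **Section 12.4:** name the van Elteren test, stratified by the V40 randomisation strata, as the radiation cohort's primary test, with the unstratified Wilcoxon test as a sensitivity analysis. Fix this without reference to unblinded results, and base the semi-annual predictive-probability futility analyses on the same test.
- **mTOR cohort:** a matching change would be for consistency only.

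The cost is one line in each section and the randomisation website set-up. No new data or patients are needed, and the sample size stays at 80. The price if V40 is not prognostic is about 0.3 points of power (80.9% against 81.2%).

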### **Unblinding Procedure:**

1. The Statistician and the investigational pharmacist will have access to the codes/assignments.

2. The codes will be revealed only if there is a safety issue and the treating physician needs to be aware of the treatment assignment.

3. The PI should be contacted regarding the patient's circumstances.

4. Prior to unblinding a patient, the investigator or research team will inform the IND Office Medical Monitor.

5. The Investigator will then give permission for the unblinding to the statistician and the investigational pharmacist.

6. The investigator or research team will notify the DSMB and IRB of the unblinding.

## Appendix A: Guidelines for Best Supportive Therapy

If patients develop mucositis or esophagitis of grade 1 for more than 5 days or grade 2 or above, the attending physician may have the option to initiate the patient on a best supportive therapy. The treatment that the Department of Investigational Cancer Therapeutics generally uses for the management of mucositis is the following:

- Xyloxylin- 1:1:1 ratio of diphenhydramine, Maalox, lidocaine; 10 milliliters (mL) swish/ swallow every 6 hours as needed)
- Caphasol (sodium phosphate; 15 mL swish/spit every 4 hours as needed)
- Valacyclovir (500 mg po TID for treatment)
- Biotene (MW every 4 hours as needed)
- Carafate (1 gm/10 mL; 10 mL swish/swallow or spit QID as needed)

